
Based on the interim results, approximately 90 evaluable subjects in the LAMA arm are required to provide >80% power to detect a 50sec change from baseline, assuming a standard deviation of 160sec and a one-sample, two-sided t-test at a significance level of 0.05. To account for a potential 25% dropout rate in Phase 2, 120 subjects will be randomized to the LAMA treatment arm.

The table below shows the number of evaluable subjects needed from the LAMA arm in Phase II to detect a 50 second change from baseline at either 80% or 90% power, given different estimates of standard deviation.

Table of one sample t test power to acted sosse change from baseline					
N needed	SD = 130	SD = 140	SD = 150	SD = 160	SD = 170
Power =80%	56	64	73	83	93
Power =90%	73	85	97	110	124

 Table 3. One-sample t-test power to detect 50sec change from baseline

As changes from baseline are not expected in a control arm, and pulmonary rehabilitation has demonstrated effects in all exercise measures in the interim analysis, these arms will serve mainly to provide additional study sensitivity data. Thus, the randomization allocation will change from 2:2:1 to 4:1:1 to make sufficient within-group comparisons. 30 subjects will be randomized to receive pulmonary rehabilitation and 30 subjects will be randomized as controls in order to provide 22 additional evaluable subjects, plus 8 more to account for a potential 25% dropout rate, in each arm. In total, 180 subjects will be randomized to Phase 2.

2. Sample size re-estimation

WP4 Exercise outcome study

The revised power calculation is aligned with the actual data from the interim analysis. This new calculation is based on a mean change in the ESWT of 60±160 seconds (as per interim analysis) with 80% power and alpha of 5%. A total of 58 subjects are required in the LAMA group and allowing for 25% attrition, a total of 78 recruited subjects are required in the LAMA (table 4). As stated above there is no specific target allocation for placebo or PR in phase 2. We propose to maintain the control arm to provide a negative control to the LAMA arm and reduce the study bias, and allow us to maintain blinding.

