Table 4: One-sample t-test power to detect 60sec change from ba	seline
---	--------

N needed	SD = 130	SD = 140	SD = 160
Power =80%	39	45	58

Randomisation allocation recruitment at Glenfield hospital, Leicester, can be seen in Table 5 (April 2015 – September 2016).

Allocation and Ratio	Control	PR	LAMA
1.2.2 (actual)	16	32	32
1.1.4 (actual)	2	2	10
Current allocated totals	18	34	42
Number required for LAMA (ESWT response of 60±160 sec with 80% power and alpha of 5	-	-	78 recruited 58 completed
New allocation for recruiting n=78 in LAMA (1:0:4)	9	0	36
Total recruited to trial	27	34	78

Table 5: Randomisation allocation over	er time
--	---------

To ensure rigor is maintained a randomisation allocation of 1:0:4 would recruit a further 9 subjects to the control group and a further 36 into the LAMA group.

Analysis Plan

All exercise test data will be analysed on a per protocol basis. All data will be assessed for normality and analysed using appropriate parametric or non-parametric statistics. Significance will be set at p<0.05 and differences will be expressed as mean and standard deviations (SD) or 95% confidence intervals.

Data will be presented as mean (SD) or median (IQR). Comparison of values obtained within the treatment(s) and the control groups will be made using a paired t test or the Wilcoxon signed rank test. All tests will be 2 tailed. Additional analysis will be done to determine the sensitivity and specificity of the other measures to detect the change in MCID. Similarly the sensitivity and specificity of the failure to detect change in the placebo will also be determined.

Reproducibility study – The baseline data will examine the test-re test reproducibility of each of the tests employed, including measures of strength. The primary variable for each test will be the conventional measure of performance. Data will be compared in two ways, firstly the intra-class correlation (ICC) will be reported and secondly limits of agreement using Bland & Altman techniques (41). The Bland & Altman plot will allow us to check the data for stability across a range of performance.

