Sensitivity study - Comparison between the exercise test outcome measures will be made at two separate time points, baseline and 6 weeks. The primary measure for each test will be the variable that is most commonly reported e.g. distance /time/peak oxygen consumption. We will assume that an MCID of 25m is meaningful for 6MWT (15), and assess the ability of other tests to predict this change. Attention will be paid to both floor and ceiling effects.

Data accumulated from individuals offered rehabilitation upon completion of either the control or LAMA arm will be analysed after the main trial has been completed. This data will allow a repeat measures analysis comparing the relative effect of two interventions upon the exercise tests. This is a secondary planned analysis.

Opportunities for sub studies

a) MCID - This study would afford the opportunity to test this assumption and identify an MCID for the exercise tests employed in this study. We will report the MCID in one of two ways, we will employ an anchor based approach and report a statistically general distribution based approach. In addition by relating observed changes in exercise performance to the CRQ we will aim to generate a further MCID for the exercise tests, since it has recently been suggested that an MCID may differ depending on the context and nature of the intervention (37).

Practical Considerations & timescale to do (plus Gant chart)

Three sites should be adequate to recruit the required number of subjects. We estimate that it would take 36 months to complete this study, the pilot study will be conducted over the first year with a recruitment target of n=50. After this pilot phase recruitment will be extended to 3 sites.

Pilot study

Allow 3 months to gain necessary recruitment approval, advertise and recruit staff. To confirm whether MHRA approval required. Completion of ethics submission.

Months 1-3	Finalise ethics approval/set up database & randomisation system with Leicester & staff training as required.	
Month 3-24	Recruit 50 subjects to study – completion of baseline measures	
Month 24-30	Completion of data collection and preliminary analysis	
Month 24-30	Change ethics for multi-centre study	
Month 30-33	Recruitment in place for other sites (2/3)	

Study extension (planned recruitment – 180 participants – 90 per site). Recruitment will continue seamlessly at the Leicester site but allow for 21 months recruitment from the end of the pilot data).

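### The only specified analysis linking one exercise test's change to another's cuts the 6MWT change at 25 m, which loses about 36% to 56% of the information (60% to 72% if the other test is cut too)

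*Protocol*

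**What the plan says.** The protocol's stated aim is to learn the relative stability and sensitivity of the exercise tests, robustly enough to inform regulators. Its hypothesis is that the 6MWT is the least sensitive of them.

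The Analysis Plan deals with change in two ways.

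- Within groups: "Comparison of values obtained within the treatment(s) and the control groups will be made using a paired t test or the Wilcoxon signed rank test", and "All tests will be 2 tailed".
- Between tests: "Additional analysis will be done to determine the sensitivity and specificity of the other measures to detect the change in MCID". The next sentence extends this to failure to detect change in the placebo group. The Sensitivity study paragraph fixes the reference: "We will assume that an MCID of 25m is meaningful for 6MWT (15), and assess the ability of other tests to predict this change".

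That paragraph also announces a comparison between the outcome measures at baseline and six weeks, but attaches no other method to it. ICC and Bland-Altman limits are for baseline reproducibility. The MCID work is a sub-study based on anchors, distribution and the CRQ. The repeated-measures analysis is secondary and compares the two interventions.

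The sample size is set on the ESWT alone (Sample size re-estimation): "A total of 58 subjects are required in the LAMA group", for a "mean change in the ESWT of 60±160 seconds". No cut-points are given for the other tests, and no precision target for sensitivity or specificity.

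**The concern.** Each exercise test's primary measure (distance, time, peak workload or oxygen uptake) gives a change on a continuous or near-continuous scale. Once the 6MWT change is cut at 25 m, a patient at +24 m counts as the opposite of one at +26 m and the same as one at -100 m. The paired tests avoid this, but they ask only whether each test moved from its own baseline. They do not say whether one test moved more than another in the same patients, which is the study's question.

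The between-test question therefore rests on an analysis in which sensitivity uses only the patients above the cut and specificity only those below it. The full-scale changes needed for a more precise answer are already being collected on the same patients. The loss would arise whichever test was the reference, so this point does not depend on whether the 6MWT is the right one.

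**Working it through.** **The plan's own figure.** For a one-sample, two-sided t test with a mean change of 60 s and SD 160 s, "with 80% power and alpha of 5"%, the normal approximation gives (160 × (1.960 + 0.842) / 60)² = 55.8, so 56. The exact noncentral-t calculation gives 58 (power 80.2%). Attrition: 58 / 0.75 = 77.3, so 78. This agrees with "allowing for 25% attrition, a total of 78 recruited subjects are required in the LAMA". The planned numbers are correct for the question they address, which is ESWT against its own baseline.

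**Inputs for the 25 m cut.** Mean 6MWT changes come from Table 1 of Power calculation (363 - 344 = 19; 429 - 415 = 14; +6 as printed). SDs of change come from the sample-size table that follows it (100, 75, 19). Changes are taken as normal.

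**Formulas.**
- Standardised cut: c = (25 - mean) / SD.
- Share at or above 25 m: p = 1 - Φ(c). Responders among LAMA completers = 58p.
- Information retained when only the 6MWT is cut: φ(c)² / [p(1 - p)]. This is the usual relative efficiency near zero correlation.
- If the other test is also cut at its median, multiply by 2/π = 0.637.
- 95% half-width for an assumed sensitivity of 70%: 1.96 × √(0.7 × 0.3 / responders).

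| 6MWT change | c | p | Responders of 58 | Retained, 6MWT cut | Retained, both cut | Half-width |
|---|---|---|---|---|---|---|
| +19, SD 100 (row adopted for the first sample size) | 0.06 | 47.6% | 27.6 | 64% | 40% | 17 points |
| +14, SD 75 (single-dose study) | 0.15 | 44.2% | 25.6 | 63% | 40% | 18 points |
| +6, SD 19 (study noted with oxitropium) | 1.00 | 15.9% | 9.2 | 44% | 28% | 30 points |

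Worked example for the last row: φ(1)² = 0.242² = 0.0586; p(1 - p) = 0.159 × 0.841 = 0.1335; ratio 0.44; × 0.637 = 0.28.

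The other two rows (+26, SD 20; +13.5, SD 2) give about 30 and 0 responders. Their printed spreads look like standard errors, so they are left out of the range.

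**Exact intervals.** An observed sensitivity of 7/9 has a Clopper-Pearson 95% interval of 40% to 97%. An observed 22/28 has 59% to 92%.

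**Is the upper case sensitive to the SD of 100?** That figure is asterisked and close to the cross-sectional SDs in Table 1 (105 and 98), so the true SD of change may be smaller. With the mean kept at +19, SD 50 gives c = 0.12 and p = 45%; SD 19 gives c = 0.32 and p = 38%, or about 22 of 58. The half-width is then 1.96 × √(0.21/22) = 19 points, within the range shown.

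**Pooling arms.** Assume 25% attrition in each arm (34 × 0.75, about 25 PR; 27 × 0.75, about 20 control), a mean PR gain of 25 to 50 m, no control change, and the same SD in all arms. Pooled responders are then about 24 to 34 with the +6/SD 19 row and about 48 to 51 with the +19/SD 100 row. At 70% sensitivity the half-widths are about 18 to 15 points and about 13 points.

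**The case against.** Four objections have weight.

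- **The low count is not the protocol's planning case.** A reader might infer that every test will be judged on about nine responders. That figure needs +6 m with SD 19 m, from a study noted as using oxitropium. For its first sample size the protocol took the SD-100 row so as not to underestimate the number needed, and that row gives about 28. Nine is the low end of a range.
- **The 58 LAMA completers are not stated to be the analysis set.** The protocol says that the PR and control arms mainly supply sensitivity data and names the placebo group for the same kind of analysis. Pooling is open, and it narrows the intervals.
- **The protocol does not say that the other tests are cut.** A reader might infer that most of the information is thrown away. That follows only if the other tests are cut too, or if responders are near 16%. Assessing the ability of other tests to predict the 25 m change could mean a ROC curve on the uncut scale, although sensitivity and specificity, as named, need a yes/no result from each test.
- **The analysis is labelled additional.** The within-group tests keep the full scale, and an SAP that is not shown may say more.

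The first three limit the size of the point, and the calculation allows for them. The last does not remove it. Additional or not, this is the one method the protocol names for relating the tests' changes, so the comment concerns a stated choice and not missing detail.

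The half-widths describe one sensitivity at a time. The tests are done on the same patients, so whether two tests can be separated depends on paired differences. The documents give no correlations from which to calculate those.

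**Conclusion.** The concern holds in a limited form. In the main trial, the only specified analysis relating one test's change to another's uses a cut scale. Cutting the 6MWT alone loses about 36% of the information at the adopted SD and about 56% in the least favourable of the usable Table 1 rows. Cutting the other test at its median as well raises the loss to about 60% to 72%. In the LAMA arm a sensitivity of 70% would carry a half-width of about 17 to 30 points; pooling arms would bring this to about 13 to 18.

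These figures rest on normal changes, Table 1 values read as SDs, near-zero correlation for the efficiency formula, an assumed 70% sensitivity, and, for pooling, assumed PR and control changes.

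The documents do not support saying that the analysis will rest on nine patients, that most of the information is necessarily lost, or that the continuous data go unused. The sample size of 58 is unaffected.

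**What to change.** In the Analysis Plan, make the main between-test comparison of change full-scale.

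1. For each test, calculate the standardised response mean (mean change / SD of change) and its difference from that of the 6MWT in the same patients. Do this separately in the LAMA, PR and control arms, with 95% intervals from a bootstrap that resamples patients. This addresses responsiveness directly and is on the scale that already sizes the trial: for the ESWT, 60 / 160 = 0.375.
2. As support, report the correlation or regression of each test's change on the 6MWT change, with confidence intervals. This cannot lead, because it shows whether two tests move together and not which one responds more.
3. In any analysis against the 25 m MCID, keep the other tests uncut: ROC curve and AUC with confidence interval.
4. Keep sensitivity and specificity at 25 m as a descriptive supplement, and state which arms are included.

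The cost is a change of wording and a few lines of analysis code, with no new data, visits or patients. A standardised difference is slightly less readable to clinicians than a responder percentage, which is why the 25 m table stays. The precision of the standardised differences depends on correlations that the protocol does not give, so 58 completers do not guarantee a clear ranking of the tests.

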Because of the lack of robust pilot data (*vide infra*) an interim analysis will be conducted once 50 subjects have completed all post intervention follow-up visits. or after recruitment of the 60th patient. One centre (Leicester) will generate phase 1 data for the sample size re-estimation prior to transition to Phase 2 (page 14). Adjustments to hypothesis will be informed from interim analysis data.

Subjects will be approached from waiting lists, clinics, rehabilitation services or departmental research databases. A patient information sheet will be given and potential participants will have at least 24 hours to consider taking part in the study. Subjects will be recruited and randomised, using a computerised randomisation service, to one of three arms as described below. Current medication will be maintained except if necessary LAMA will be withdrawn 2 weeks prior to baseline measurements and replaced with SAMA in the group randomised to the pharmaceutical bronchodilator arm. For those participants not on a LAMA upon recruitment, but with an FEV₁ less than 50% predicted a LAMA will routinely be prescribed. This is in accordance with the updated NICE COPD guidelines² (recommendation U7).

Exercise tests selected are shown below:-

1. Laboratory

- Maximal incremental symptom-limited cycle ergometer cardio-pulmonary exercise test
- Endurance cycle exercise test: Constant work load (85% maximum peak workload achieved during maximal CPET) at a target of rpm 60.

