Subjects will perform a maximal symptom-limited incremental exercise test on an electrically-braked cycle ergometer (ramp protocol, increments 10Watts/minute) and an endurance cycle test conducted at 85% of peak workload. Ventilation and gas exchange measurements will be made throughout the exercise tests using a breath-by-breath computerised system³. Initial, end-exercise, 3 minutes recovery and during loaded testing (every 2 minutes), the Borg breathlessness Score, RPE Score will be recorded along with reason for termination.. The same variables will be collected pre and post intervention/control periods and iso-time data with respect to peak performance measures on the initial assessment will be reported on post intervention measurements. All inhalers will be withheld for 6 hours prior to measurements. Other medications will remain unchanged. The variables reported from these laboratory based tests will be those conventionally reported and will include peak workload (watts), peak oxygen uptake (ml/min/kg) and ventilation (l/min). For the endurance test, exercise time will be an additional important outcome (secs). Prior to, upon completion and 3 minutes into recovery of laboratory testing, measures of HR, percutaneous oxygen saturation and BP will be recorded. Patient's safety and termination of testing will be conducted in accordance with ATS/ACCP (23).

2. Field based

Prior to and upon completion of the field based tests, measures of breathlessness, perceived exertion (Borg scores), HR, BP, and percutaneous oxygen saturation will be recorded. In addition the reason for termination (leg fatigue, SOB or combination) will be reported.

² http://publications.nice.org.uk/chronic-obstructive-pulmonary-disease-cg101

³ Glenfield uses a Medisoft ergocard gas analyser and Expair Software.

- 6 MWT this will be conducted along a 30 or 50m corridor according to the ATS guidelines (24). Encouragement will be standardised and a practice walk completed. Conventionally the output from the 6MWT is expressed in metres. We will record the number and duration of any breaks in walking taken by the patient. A total of 3 tests will be required (1 at visit 1 and 2 at visit 2) in order to test repeatability following familiarisation, before intervention.

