Six week bronchodilator therapy (LAMA; Tiotropium). It is likely that a significant number of subjects recruited for this trial will have already been prescribed Tiotropium in line with NICE guidelines, and these subjects, if randomised to this arm, will be required to withdraw from this for a period for a two week washout. Tiotropium will be replaced by the prescription of a short-acting muscarinic antagonist bronchodilator therapy (SAMA) for this two week washout. These subjects will then recommence inhaled Tiotropium following baseline testing at visits two and three.

For subjects recruited but prescribed a LAMA combination inhaler the prescription will be amended to reflect the above washout though replacing any inhaled long-acting beta₂ adrenergic receptor agonists or corticosteroids with the recommended alternative along with the above described SAMA and for the duration of the washout phase. Following this two week period, baseline measures will be conducted as described above. This will afford the opportunity to observe the possible detrimental effect of withdrawing Tiotropium. After reassessment of six weeks of regular bronchodilator therapy with Tiotropium (plus replacement alternatives) all outcome measures will be repeated. If subjects have not previously been prescribed a LAMA they will continue with any current prescribed inhaler therapy and if randomised to LAMA will commence the 'LAMA' arm of the trial after visit 3. Inhaler technique will be assessed and confirmed to be acceptable. Any changes in prescription will be notified to the subjects General Practitioner/Respiratory physician where future care provision will be assessed.

Intervention 2

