For each exercise test conducted in the laboratory an online gas analysis system will be employed. This will not be possible for field based exercise tests. The following baseline variables will be collected for all tests, not necessarily all on every occasion but where appropriate documented at every visit.

- 1. Baseline spirometry (lung volumes and diffusing capacity of the lung for carbon monoxide (DLCO) to be done at entry only)
- 2. Height/weight (BMI)/leg length(ASIS to Medial Malleolus)
- 3. Fat free mass index by bio-electrical impedance⁶
- 4. Resting Heart rate
- 5. Resting fingertip oxygen Saturation
- 6. MRC dyspnoea score
- 7. Resting Borg breathlessness & RPE Scale

At the start and end of each exercise test, as well as all performance measures we will record-

- 1. Saturation
- 2. Heart rate
- 3. Blood pressure
- 4. Borg breathlessness & leg exertion
- 5. Reason for termination
- 6. For the 6MWT we will record the number and time of stops.

At baseline and after 6 weeks the exercise tests will be conducted over 4 visits following a day of familiarisation.

Visit 1 (1 day visit or split over 2 consecutive days) – Familiarisation

Consent and Eligibility confirmation

⁵ So as a secondary aim possibly generating insights into order effects

⁶ Glenfield use Bodystat[®] 1500.

Subjects will be given the opportunity to attend the initial consent and eligibility screening (including spirometry) prior to committing to a whole or half day of testing.

- 1. Informed consent secured
- 2. Spirometry (gas transfer and full lung function test)
- 3. Individuals will be randomised to one of three groups as described in figure 1.
- 4. Baseline questionnaires
- 5. Apply physical activity monitors
- 6. Isometric muscle strength (QMVC)
- 7. Exercise testing will be completed in random order. There will be a minimum of 30 minutes rest between each test, in addition two activity monitors will be given to the individual, to be worn for 14 days (24 hours a day). These will also be worn during exercise testing for visits 1, 2, 3, 4 and 5 to gauge intensity and energy expenditure.
 - Maximal cardiopulmonary cycle test & Endurance cycle test
 - 6 MWT (practice)
 - ISWT (practice) & ESWT (practice)
 - SPPB

Visit 2 (two weeks later, after activity monitor data collection period) - Baseline

Exercise tests will be presented in random order. There will be at least 30 minutes rest between each test.

- a. Maximal incremental cardiopulmonary cycle test

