- b. 6 MWT (performed twice with a 30 min rest in-between)
- c. ISWT (performed twice with a 30 min rest in-between)
- d. Strength testing (QMVC)

Visit 3 (next day)

Three exercise tests will be conducted in random order. There will be at least 30 minutes rest between each test.

- e. ESWT (85% peak performance)
- f. Cycle endurance test (85% peak performance)
- g. SPPB

Retesting after completion of the 6 week intervention (visits 4 and 5), will comprise the following measures presented in the same order as baseline (visits 2 and 3). These tests will be completed by a blinded assessor, blind to the intervention and previous results. Two activity monitors will be given, to be worn during visits 4 & 5 and for a further 7 days (24 hours a day).

- 1. ISWT
- 2. 6MWT
- 3. ESWT, at same level as baseline
- 4. Maximal incremental cycle test
- 5. Endurance cycle test, at same workload level and RPM as baseline
- 6. SPPB
- 7. Strength testing (QMVC)
- 8. Health Questionnaires

At the completion of the interventions a global rating scale of change will be reported for each exercise test. This will allow the description of the MID using anchor and distribution based methods. The global rating scale will identify two levels of change (a little improvement and a greater level of improvement). The scale employed will be one recently described by Pepin et al (37) describing the MCID for the ESWT.

Power calculation

In order to calculate a sample size a literature search was conducted using the search terms Tiotropium and six minute walk (and variants e.g. 6MWT) to identify studies giving an estimate of the likely benefit of the drug. Results found are shown in Table 1.

n	Blinded Assessor	Baseline 6MWT (mean (SD))	Tiotropium 6MWT (mean (SD))	Reference	notes
30	n	344 (105)	363 (98)	Fernandes 2010 (38)	Additional use of LABA
38	У	490 (67)	+6 (19)	Oga 2000 (12)	Additional use of Oxitropium
41	n	403 (20)	429 (17)	Fujimoto (39)	-
38	n	222 (5)	+13.5 (2)	Um(40)	-
44	У	415 (75)	429 (70)	Okudan(21)	Single dose (after 120 minutes)

Table 1: Properties of trials investigating Tiotropium with the 6MWT.

Based on these data [name] (Statistician to the Royal Brompton hospital Biomedical Research Unit) estimated the following sample sizes for achieving an increase in 25m in 6MW with 80% power and p=0.05.

Reference	Tio 6MWT (SD of Change From BL)	Estimated Sample size
Fernandes 2010	100 *	128
Oga 2000	19	7
Fujimoto	20 *	7
Um 2007	2	1
Okudan 2006	75 *	73

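### Test-retest stability is measured over unlike intervals: five tests rely on a two-week pair that spans the LAMA washout in some participants, while 6MWT and ISWT have same-day pairs

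*Protocol*

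**What the plan says.** The Reproducibility study paragraph of the Analysis Plan states: "The baseline data will examine the test-re test reproducibility of each of the tests employed, including measures of strength". It names ICC and Bland-Altman limits of agreement and sets no restriction by arm or by change of inhaler.

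The Field based section gives 6MWT and ISWT three tests each, "in order to test repeatability following familiarisation, before intervention". At Visit 2 the listing reads "6 MWT (performed twice with a 30 min rest in-between", with the same arrangement for ISWT. The remaining tests appear once at Visit 1 and once at Visit 2 or 3; for example, Visit 3 lists "ESWT (85% peak performance" once.

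On treatment:
- Randomisation is at Visit 1: "Individuals will be randomised to one of three groups as described in figure 1".
- The recruitment text before the list of exercise tests says "Current medication will be maintained except if necessary LAMA will be withdrawn 2 weeks prior to baseline measurements", with a SAMA substituted, in the LAMA arm.
- Intervention 1 has these participants restart tiotropium after testing at Visits 2 and 3, and says of the washout: "This will afford the opportunity to observe the possible detrimental effect of withdrawing Tiotropium".
- For participants not on a LAMA at recruitment, the same recruitment text says that with an FEV1 "less than 50% predicted a LAMA will routinely be prescribed". It does not say when.

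**The concern.** The Aim names relative stability, alongside sensitivity, as a property on which the tests are to be compared, to guide the choice of trial outcomes. That needs retest pairs collected under like conditions.

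Here a lower ICC or a non-zero Bland-Altman mean difference for, say, ESWT than for 6MWT could arise from the longer interval, from learning after a first exposure, or from stopping tiotropium, and not from the test. In washed-out participants the same interval is asked to do two jobs: show the effect of withdrawal and show stability under unchanged conditions. Learning would probably raise Visit 3 performance and withdrawal lower it, so a pooled mean difference near zero could hide both.

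**Working it through.** **1. Pre-intervention tests by visit** (visit lists and Schedule of Visits; Visit 1 is Day 0 or Days 0 and 1, Visit 2 is Day 14, Visit 3 is Day 15).

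| Test | Visit 1 | Visit 2 | Visit 3 | Pairs available |
|---|---|---|---|---|
| Incremental cycle | 1 | 1 | – | Visit 1 to 2 only |
| QMVC | 1 | 1 | – | Visit 1 to 2 only |
| Endurance cycle | 1 | – | 1 | Visit 1 to 3 only |
| ESWT | 1 | – | 1 | Visit 1 to 3 only |
| SPPB | 1 | – | 1 | Visit 1 to 3 only |
| 6MWT | 1 | 2 | – | same-day pair, and Visit 1 to 2 |
| ISWT | 1 | 2 | – | same-day pair, and Visit 1 to 2 |

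**2. Washout against these pairs.** Randomisation at Visit 1, withdrawal for the two weeks before baseline and restart after Visit 3 put Visit 1 before the washout and Visits 2 and 3 at its end. The single pair for each of the five tests spans the change. Both tests of the same-day 6MWT and ISWT pairs fall after it.

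**3. Size of the LAMA arm.** The protocol's figure reproduces: for a 60 s change, SD 160 s, two-sided alpha 5%, a one-sample t-test has 80.2% power at n = 58, and 58/0.75 = 77.3, so 78 recruited. Table 5 totals 27 + 34 + 78 = 139. The LAMA share is 78/139 = 56%.

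**4. Share of pairs affected.** The protocol expects many participants to be on tiotropium already but gives no proportion. Assume 25% to 75% of the LAMA arm is washed out: 0.25 × 78 = 19.5 to 0.75 × 78 = 58.5 people, so p = 19.5/139 = 0.140 to 58.5/139 = 0.421 of all pairs.

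**5. Illustration for ESWT.** Assume a withdrawal loss d of 30 to 60 s, and an SD of retest differences of 80 to 160 s without withdrawal. The interim LAMA-arm gain of 59 s makes the upper loss plausible but does not establish it.
- Mean shift, p × d: 0.140 × 30 = 4.2 s to 0.421 × 60 = 25.3 s.
- 95% half-width of the mean difference, 1.96 × SD/√139: 13.3 s (SD 80) to 26.6 s (SD 160).
- Added variance, p(1 − p)d²: 108.5 to 877.5 s². Limits widen by √(1 + added/SD²) − 1: 0.2% (108.5, SD 160) to 6.6% (877.5, SD 80).
- ICC, starting from 0.90 (assumed), worst case p = 0.421, d = 60. At SD 80 the within-person variance is 6400/2 = 3200 and the between-person variance 28,800. The mean squared difference becomes 6400 + 0.421 × 3600 ≈ 7916, so the ICC is 28,800/(28,800 + 3958) = 0.879. At SD 160 it is 115,200/(115,200 + 13,558) = 0.895.

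**6. Precision after restriction.** Fisher z with SE = 1/√(n − 1.5), ICC 0.90 assumed:

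| Pairs | 95% CI |
|---|---|
| 139 (all recruits) | 0.86 to 0.93 |
| 119 (25% of LAMA arm washed out) | 0.86 to 0.93 |
| 80 (75% washed out) | 0.85 to 0.93 |
| 61 (control and PR only) | 0.84 to 0.94 |
| 30 (about half of those 61, if LAMA starts remove the rest) | 0.80 to 0.95 |

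The count of 139 is recruitment, so complete pairs will be somewhat fewer.

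**7. A second condition for a clean pair.** ESWT speed is set from the ISWT and the endurance cycle load from the incremental test, and both source tests are repeated at Visit 2. The protocol requires the same level as baseline only after the intervention. Visit 1 and Visit 3 endurance tests may therefore differ in speed or load, even in participants whose treatment did not change.

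**The case against.** The best reply is that choosing the participants and pair for an ICC is ordinary SAP work, that the SAP is not at hand, and that Intervention 1 shows the investigators knew the interval was a withdrawal interval. That stands in part: the SAP may restrict the analysis. But the number and timing of tests are fixed in the protocol, its Power calculation section says the analysis plan is as set out below, and the text below applies the analysis to every test without restriction. If baseline data means Visits 2 and 3 only, the five tests have no retest pair at all, so that reading does not help. The interim section's reference to repeatability at the initial visits favours the Visit 1 to Visit 3 reading for ESWT.

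The second reply is that the effect is small and every input assumed. This largely stands. Against the limits of agreement themselves (1.96 × 80 = 157 s to 1.96 × 160 = 314 s), a 4 to 25 s shift is about 1% to 16%. It is also below the lowest ESWT MCID the protocol mentions, 45 s, and the worst-case ICC of 0.88 lies inside the 139-pair confidence interval.

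Third, no formal between-test comparison of ICCs is planned, and the hypothesis concerns sensitivity. True, but the Aim still sets the tests side by side on stability.

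A reader might also infer that the choice of ESWT for the sample size re-estimation is undermined, since its repeatability was cited in support. The protocol does not say which participants or pairs lay behind that statement, and the recalculation itself uses the change after treatment.

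**Conclusion.** The mismatch is real and follows from the protocol alone: five tests are assessed on two-week pairs starting at the familiarisation visit, and two can be assessed on same-day pairs after it. That applies in every arm and needs no assumption. The treatment change within the five-test pairs is equally clear in structure, but it concerns only an unknown part of the LAMA arm.

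For ESWT the likely consequence is mainly a shift in the mean difference, within noise at the low end and comparable to or larger than its confidence half-width at the high end, with little change in the limits or ICC. All of this rests on the assumed washed-out share, withdrawal loss, SD and ICC shown above.

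Two stronger readings are tempting and not supported. One is that withdrawal materially distorts all five tests: nothing in the protocol shows an effect on SPPB or QMVC, where it may be negligible, and the cycle tests are not quantified. The other is that the response analysis is compromised: it runs from Visits 2 and 3 to Visits 4 and 5 and does not use the Visit 1 pair. This should be corrected, but it does not threaten the trial's main result.

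**What to change.** 1. For incremental cycle, endurance cycle, ESWT, SPPB and QMVC, make the primary ICC and limits of agreement those from participants whose inhaled treatment was unchanged between Visit 1 and Visits 2/3. These are control and PR participants plus LAMA-arm entrants not on a LAMA, less anyone started on a LAMA in that interval. Report washed-out participants separately as the withdrawal comparison.
2. For ESWT and endurance cycle, use only pairs done at the same speed or workload at Visit 1 and Visit 3.
3. For the between-test comparison, also compute 6MWT and ISWT reproducibility from Visit 1 against the first Visit 2 test in the same participants, and show the same-day pairs alongside.

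No visit or test is added. The cost is fewer pairs and somewhat wider intervals, as tabulated above; step 2 may remove more pairs, by a number the protocol does not allow one to estimate. If LAMA starts for low FEV1 fall in the interval, their exclusion would remove more severe patients and narrow the range on which an ICC depends. Learning from the first exposure remains in the Visit 1 pairs: step 3 puts all seven tests on a comparable interval but does not remove it.
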